6.2 Other treatment(s)

6.2.1 Concomitant therapy

The investigator should instruct the patient to notify the study site about any new medications he/she takes after the patient is enrolled into the study. All medications, procedures, and significant non-drug therapies (including physical therapy and blood transfusions) administered after the subject is enrolled into the study must be recorded on the appropriate Case Report Forms (CRFs).

Each concomitant drug must be individually assessed against all exclusion criteria/prohibited medication. If in doubt, the investigator should contact the Novartis medical monitor before randomizing a subject or allowing a new medication to be started. If the subject is already enrolled, contact Novartis to determine if the subject should continue his/her participation in the study.

6.2.1.1 Permitted concomitant therapy requiring caution and/or action

Investigators may prescribe concomitant medications or treatments deemed necessary to provide adequate supportive care except for those medications identified as "prohibited" as listed in Table 6-3. Specifically, subjects should receive full supportive care during the study, including treatment with antibiotics, anti-emetics, anti-diarrheals, analgesics, and other care as deemed appropriate, and in accordance with their institutional guidelines. In addition to the background asthma medications and rescue medications described in Section 6.1.2, the following concomitant medications related to asthma/allergy treatment are permitted from screening through the follow-up period.

	Table 6-1	Medications	allowed under	certain	conditions
--	-----------	--------------------	---------------	---------	------------

Class of medication	Condition
Topical corticosteroids for the treatment of eczema	In recommended doses and dosage regimens
Intra-nasal corticosteroids	Stable dose for at least 1 month prior to Screening. In the case of as needed, provided an established pattern of use has been documented.
Systemic corticosteroids	To treat asthma exacerbations
Topical antihistamines	In recommended doses and dosage regimens
Oral antihistamines	Stable dose for at least 1 month prior to Screening and throughout the trial.
	In the case of as needed, provided an established pattern of use has been documented
Topical, nasal, and/or ocular formulations of cromones	In recommended doses and dosage regimens
Maintenance immunotherapy for allergies	Stable dose for at least 3 months prior to run-in visit and unchanged throughout study treatment.
COVID-19 vaccination	At least one week before an in-clinic visit

Table 6-2 Medications to be withheld prior to spirometry

Class of medication	Last dose prior to spirometry
Short-acting β ₂ -agonists (SABA)	≥ 6 hours
Long-acting β_2 -agonists (LABAs) given twice daily	≥ 24 hours
ICS-Formoterol given PRN	≥ 24 hours
LABAs given once daily (e.g. vilanterol, indacaterol)	≥ 36 hours
Long-acting muscarinic antagonists (LAMAs e.g. tiotropium)	≥ 7 days
Fixed-dose combinations of LABA and ICS given twice daily	≥ 24 hours
Fixed-dose combinations of LABA and ICS given once daily	≥ 36 hours
Fixed-dose combinations of LABA and LAMA and ICS given once daily or twice daily.	≥ 2 days

The treatment of asthma exacerbations including the initiation of systemic corticosteroids should be done according to investigator's or treating physician's medical judgement and should be in line with their institutional, national and international recommendations. If systemic corticosteroids are required, a patient may return to the study assessments after successfully completing an Oral Corticosteroid (OCS) taper. If patients require treatment with systemic steroids longer than 3 weeks, including taper, or chronic systemic steroid administration, they must be discontinued from treatment.

If indicated for the treatment of an adverse event, including asthma exacerbation, any treatment (including medications in Table 6-3) deemed necessary by treating physician for the safety of the patient is allowed from the start of the event until the event is resolved. If it is transitioning to chronic treatment, the investigator should discuss with Novartis Medical Monitor. Patients may NOT self-medicate (other than administration of rescue medication) or adjust therapy without permission/guidance from treating physician.

6.2.2 Prohibited medication

The specified minimum washout periods prior to the run-in are described in Table 6-3. Use of the treatments displayed in Table 6-3 is NOT allowed after the beginning of run-in (unless for the treatment of adverse events and asthma exacerbations). Each concomitant drug must be individually assessed against all exclusion criteria and the tables below to see if it is allowed. If in doubt, the investigator must contact the Novartis medical monitor or designee before randomizing a patient or allowing a new medication to be started. Medications must be assessed for adherence to the indication and other inclusion/exclusion criteria.

Class of medication	Minimum cessation prior to Run-In ^{1,2}
Other investigational drugs	30 days or 5 half-lives, whichever is longer
Live attenuated vaccine*	2 days
Inactivated influenza vaccination, pneumococcal vaccination or any other inactivated vaccine*	2 days
Short-acting anticholinergics (SAMA)	6 hours
Long acting muscarinic antagonists (LAMAs)*	7 days
Fixed combinations of short-acting β_2 agonists and short-acting anticholinergics (SABA/SAMA)	12 hours
Xanthines*	7 days
Leucotriene Receptor Antagonists (LTRAs) and leucotriene synthesis inhibitors*	7 days
Systemic mast cell stabilizers (e.g., cromoglycate, nedocromil, ketotifen)*	7 days
Oral corticosteroids	6 weeks
Short-acting, intra-articular, intramuscular, intravenous corticosteroid	6 weeks
Long acting, intra-articular, intramuscular depot corticosteroids	3 months and 2 weeks
Monoclonal antibodies for the treatment of asthma (e.g. omalizumab, mepolizumab, benralizumab etc.) (investigational or approved)	5 half-lives or 6 months, whatever is longer
Other anti-TSLP drugs (investigational or approved)	Not permitted
Methotrexate, gold salts, cyclosporine, troleandomycin, azathioprine, other immunomodulator drugs or immunomodulatory monoclonal antibodies	6 months

Table 6-3Prohibited medication

¹ This table is not considered all-inclusive. Medications should be assessed for adherence to the indication and other inclusion/exclusion criteria

² These medications are also prohibited if administered for other indications

*these medications can be used again in the follow up period

6.3 Subject numbering, treatment assignment, randomization

6.3.1 Subject numbering

Each subject is identified in the study by a Subject Number (Subject No.), that is assigned when the subject is first enrolled for screening and is retained as the primary identifier for the subject throughout his/her entire participation in the trial. The Subject No. consists of the Center Number (Center No.) (as assigned by Novartis to the investigative site) with a sequential subject number suffixed to it, so that each subject is numbered uniquely across the entire database. Upon signing the informed consent form, the subject is assigned to the next sequential Subject No. available.

6.3.2 Treatment assignment, randomization

At the end of run-in, prior to the first dosing of the Investigational Medicinal Product (IMP), all patients will have 2 spirometry assessments done i.e. at -2h45min and -2h15min timepoints. Prior to randomization the patient's spirometry assessments will be evaluated by a Central overreader and site staff will be informed if both spirometry assessments are acceptable. Subjects must have an FEV1 value of $\geq 40\%$ and $\leq 85\%$ of the predicted normal shown in both spirometry assessments in order to be randomized. If both spirometry assessments of a patient are evaluated by the overreader as unacceptable or the average FEV1 predicted value from both spirometry assessments differs >15% (absolute value) from the beginning of run-in FEV1 predicted value, the randomization visit must be stopped and the patient must not be randomized on that day. The patient should return for an ad hoc randomization visit on the following day or as soon as possible and complete all assessments. If the difference in FEV1 predicted value between the beginning of Run-in and this ad hoc randomization visit is still > 15%, this patient must be excluded from the study. This patient is not allowed rescreening.

At the end of run-in visit, all eligible subjects will be randomized via Interactive Response Technology (IRT) to one of the treatment arms. The investigator or his/her delegate will contact the IRT after confirming that the subject fulfills all the inclusion/exclusion criteria. The IRT will assign a randomization number to the subject, which will be used to link the subject to a treatment arm and will specify a unique medication number for the first package of study treatment to be dispensed to the subject.

The randomization numbers will be generated using the following procedure to ensure that treatment assignment is unbiased and concealed from subjects and investigator staff. A subject randomization list will be produced by the IRT provider using a validated system that automates the random assignment of subject numbers to randomization numbers. These randomization numbers are linked to the different treatment arms, which in turn are linked to medication numbers. A separate medication list will be produced by or under the responsibility of Novartis

Global Clinical Supply (GCS) using a validated system that automates the random assignment of medication numbers to packs containing the study treatment.

Randomization will be stratified by peripheral blood eosinophil counts at the screening visit (< $300 \text{ cells/}\mu l \text{ or } \ge 300 \text{ cells/}\mu l$). Treatment randomization will also be stratified at the regional level.

The randomization scheme for subjects will be reviewed and approved by a member of the Randomization Office.

6.4 Treatment blinding

This study consists of a single-blind run-in period (i.e., only patients will be blinded to the identity of the treatment) followed by a double-blind randomized treatment period.

Subjects, investigator staff, persons performing the assessments, and CTT will remain blind to the identity of the treatment from the time of randomization until database lock, using the following methods:

(1) Randomization data are kept strictly confidential until the time of unblinding and will not be accessible by anyone else involved in the study with the following exceptions: independent statistician and programmer supporting the DMC and, if deemed necessary by the DMC, the DMC members.

(2) the identity of the treatments will be concealed by the use of study treatment that are all identical in packaging, labeling, schedule of administration, appearance, taste, and odor.

The randomization codes associated with subjects from whom PK samples are taken will be disclosed to PK analysts who will keep PK results confidential until database lock.

Unblinding will occur in the case of subject emergencies, in case of a DMC request as an outcome of their evaluation and at the conclusion of the study.

If sponsor decides to conduct an unblinded interim analysis for internal decision making (Section 4.4), unblinding of predetermined CTT members may occur at the time of interim analyses. The study may then continue under the management of a separate blinded team. In order to maintain the integrity of the study data, separate blinded team members will not have access to any unblinded data. The detailed procedures will be described in a separate charter. The remainder of the members including clinical study team, subjects, investigator staff, persons performing the assessments will also remain blinded.

6.4.1 Independent study-treatment administration site staff member

Owing to a slight difference in capsule powder fill volume between CSJ117 doses and placebo, none of the site staff including the OHP, apart from the independent study-treatment administration site staff member should handle or see the Investigational Medicinal Product (IMP) capsules when assisting patient with administration. An independent study-treatment administration site staff member familiar with the correct inhalation technique will be the only person responsible for assisting patients with removing capsules from their blisters and placing them in the Concept1 inhaler if required and for the onsite IMP administration. The training kit

can be handled by the assigned study site staff for patient training purposes. The OHP must be familiar with the correct inhalation technique, observe the patient inhalation and if necessary retrain the patient on correct inhalation technique but must not directly handle or see the IMP capsules.

Appropriate measures must be taken by the independent study-treatment administration staff to ensure that no information regarding the IMP capsules is discussed with the site staff or OHP and that the site staff do not come into direct contact with the IMP capsules. The independent study-treatment administration staff will not perform any other study related duties (including assessments, procedures, documentation, data collection or record keeping for the study).

Note: the risk of subject unblinding due to the different appearance of capsules is negligible as it is not expected subjects will see other individuals' patient kits. Besides the independent study-treatment administration site staff member, other team members are not allowed to handle or see the IMP capsules directly.

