This estimand is considered appropriate for a dose finding trial in order to obtain a clear dose response signal and understand the maximum potential effect of the drug.

3 Study design

This study is a phase IIb, multicenter, multi-national, double-blind, randomized, parallel-arm, placebo-controlled study to evaluate the effect of 5 dose levels of CSJ117 in adult subjects with inadequately controlled asthma despite medium to high dose ICS plus LABA. Approximately 625 patients will be randomized into this study. A sample size re-estimation might be performed strictly using the blinded data after approximately 150 high eosinophils subjects completed the week 8 visit.

The study will include:

• A screening period of approximately 2 weeks, or shorter, to assess eligibility and baseline EOS count. Screening may optionally be split across 2 days to allow the collection of laboratory samples and the laboratory evaluations including the blood eosinophil (EOS) counts first. Patients will replace their current rescue medication with SABA provided by

Novartis, wash out prohibited medications (see Table 6-3) and practice the electronic peak expiratory flow (ePEF) and eDiary device. Screening must not end before confirmation of EOS count. If the results of EOS count or other laboratory assessments are not available at the end of the 2-week screening period or reversibility was not demonstrated at the run in visit the screening period will be extended.

- A single blinded placebo run-in, i.e. Baseline, period of approximately 4 weeks, to collect • baseline data for efficacy variables and compliance with the ePEF and eDiary device as well as to assess adherence with placebo and standardized maintenance medication, fluticasone propionate/salmeterol xinafoate 250/50 µg or 500/50 µg b.i.d.. If a patient experiences an asthma exacerbation or respiratory tract infection (RTI) during the run-in period, the run-in period must be extended to 8 weeks to allow for resolution of the asthma exacerbation or respiratory tract infection before randomization. Eligibility for randomization will be determined at the end of the placebo run-in period. Site staff should not inform patients that during run-in they will receive placebo.
- A double blinded treatment period of 12 weeks. •
- A follow-up period of 12 weeks, study drug free, following the last dose of study drug. •

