6. Subjects must perform a reversibility test at the run-in visit. Reversibility is demonstrated by a Post-BD reversibility of FEV1 $\geq 12\%$ and ≥ 200 mL within 30 minutes after administration of 400 µg salbutamol/albuterol (or equivalent dose). If reversibility is not demonstrated at the run-in visit (FEV1 increase was lower than 12% and 200 mL or pre-BD or post-BD spirometry tests were assessed by the central over reader as unacceptable) reversibility will be attempted at up to two ad hoc, unscheduled separate visits (the second ad hoc visit is allowed only for patients who failed to show positive reversibility during the first ad hoc visit).

If reversibility is not demonstrated at run-in visit nor the unscheduled separate visits, but both pre and post-BD efforts within the same run-in or permitted unscheduled session are confirmed acceptable by central spirometry overread, the following historical information may be used:

• Documented evidence of reversibility that was performed according to ATS/ERS guidelines (ATS/ERS 2019) within the 1 year prior to Screening. Where a patient is assessed as eligible based on historical evidence of reversibility, a copy of the original printed spirometry report with relevant spirometry tracings must be available as source documentation.

Until reversibility is demonstrated patient must continue the screening period or be run in failed, if they do not wish to continue the trial. Use of a spacer device is allowed ONLY for reversibility testing (See section 6.1.2.1).

- 7. Subjects must have an ACQ-5 score of ≥ 1.5 at screening and end of run-in visits.
- 9. Subjects must meet all of the following criteria at end of run-in visit (Week 0, Day1) prior to randomization:
 - 1. Subjects must demonstrate acceptable inhaler, peak flow meter, and spirometry techniques during the run-in period (from beginning to end of run in) as judged by the investigator.
 - Subjects must demonstrate ≥ 70% compliance with the asthma controller fluticasone propionate/salmeterol during the run-in period based on their inhaler use count. 70% compliance is defined as at least one dose of medication i.e. morning or evening dose, taken in 70% of the days spent in the run-in period.
 - 3. Subjects must demonstrate $\geq 70\%$ compliance with the CSJ117 placebo/Concept1 during the run-in period based on capsule use count. 70% compliance is defined as medication taken in 70% of the days spent in the run-in period.

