6.6 Additional treatment guidance

6.6.1 Treatment compliance

The time of study treatment administration at each dosing visit will be collected on the eCRF as well as any dosing interruptions. For visits where spirometry is performed, time of dose should be taken from the spirometer. While at home administration of study medication and background treatment will be recorded by eDiary during the placebo run-in period and the treatment period. The data from the eDiary will be reviewed at each visit.

Study treatment compliance should be assessed by the investigator and/or center personnel at least for all visits. Where necessary, the Investigator will discuss compliance/documentation issues with the patient. The Investigator or designee, including OHP, will collect the

used/unused study medication and packaging (unused capsules/blister strips DPIs) at all visits. Study treatment compliance will be assessed based on the capsule count from the blisters dispensed at the previous visit.

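### Protocol Sections 6.4, 6.4.1 and 6.6.1 conflict on capsule appearance and on who may see returned capsules, leaving a possible but unquantified risk to the blind

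*Protocol*

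**What the plan says.** Protocol Section 6.4 gives, as its second method of blinding, "study treatment that are all identical in packaging, labeling, schedule of administration, appearance, taste, and odor".

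Section 6.4.1 creates an independent administrator at each site. Its stated reason begins "Owing to a slight difference in capsule powder fill volume between CSJ117 doses and placebo". No other site staff, and explicitly not the OHP, may handle or see the capsules. On separation of roles it says: "The independent study-treatment administration staff will not perform any other study related duties"; assessments, data collection and record keeping are among the examples. The section closes with a note that "the risk of subject unblinding due to the different appearance of capsules is negligible". The only reason it gives is that patients should not come across one another's kits.

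Section 3 describes the period before randomization as "A single blinded placebo run-in, i.e. Baseline, period of approximately 4 weeks", and tells staff not to disclose to patients that it is placebo. Inclusion criterion 9 in Section 5.1 requires at least 70% compliance by capsule count, meaning "medication taken in 70% of the days spent in the run-in period".

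Section 6.6.1 has the investigator or a designee, the OHP included, collect "used/unused study medication and packaging (unused capsules/blister strips DPIs) at all visits". The investigator or center personnel assess compliance, and the measure is the capsule count.

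**The concern.** There are two separate problems.

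The first concerns patients. The reassurance in Section 6.4.1 deals with a comparison between patients. The comparison that every patient can make is within person: run-in capsule against double-blind capsule. The plan does not discuss it.

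The second concerns staff. Section 6.4.1 keeps capsules out of the sight of those who run assessments. Section 6.6.1 then hands returned capsules to those same people, and the one person allowed to see capsules is excluded from the task. A site that follows 6.6.1 breaks 6.4.1.

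What is at stake is the credibility of the blind for outcomes that depend on the patient's report or effort. ACQ-5 and AQLQ+12 are self-reported, and the SAP still models both (Sections 2.7.1.2 and 2.7.1.4). The primary endpoint is FEV1, and Section 16.3 of the protocol describes spirometry as dependent on effort and careful instruction.

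**Working it through.** The plan gives no figure for this risk, so there is none to reproduce. The check is a comparison of the texts, with one piece of arithmetic for scale.

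**1. Appearance.** Section 6.4 claims identity of appearance. Section 6.4.1 reports a fill difference and itself speaks of capsules that look different. Both statements cannot stand.

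**2. What the patient has seen before Day 1.** The planned run-in is 28 days, and 70% of 28 is 19.6, so about 20 days of placebo capsules at minimum in a run-in of planned length. The run-in becomes 8 weeks after an exacerbation or respiratory tract infection. Section 6.6.1 shows that some of this dosing is at home.

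**3. How many patients then change capsule.** Allocation is 2:1:1:1:2:2, which sums to 9.
- Placebo: 2/9 = 22.2%. Active: 7/9 = 77.8%.
- Planned 625: 625 × 2/9 ≈ 139 placebo and 625 × 7/9 ≈ 486 active.
- The 335 enrolled (SAP Section 1.1), if allocated in the planned ratio: 335 × 2/9 ≈ 74 and 335 × 7/9 ≈ 261.

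These are the numbers who could be in each situation, not the numbers who noticed anything. For a patient to learn something from the change, the fill must be visible in ordinary use, and run-in placebo must match double-blind placebo. The documents state neither. Even then, the patient has not been told that the earlier capsule was placebo.

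**4. Whether the staff instructions can all be followed.**
- Collecting returns: 6.6.1 assigns this to the investigator or a designee, including the OHP; 6.4.1 bars the OHP and all staff except the administrator from handling or seeing capsules.
- Counting: 6.6.1 bases compliance on the capsule count and gives the assessment to the investigator or center personnel; the same bar applies.
- Reading designee as the independent administrator does not resolve this, because 6.4.1 excludes that person from data collection and record keeping.

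Staff also have a reference capsule. Under Section 6.4 only patients are blinded during run-in, and 6.4.1 lets site staff handle the training kit, which Section 6.7.2 says contains placebo capsules.

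**5. When exposure could matter.** Table 16-4 places the Concept1 compliance check at time 0, after that visit's questionnaires, FeNO and both pre-dose spirometry tests. A count therefore cannot influence the same visit. It could carry over: checks at Weeks 2 and 4 precede the Week 8 assessment, and checks at Weeks 2, 4 and 8 precede Week 12. Those two visits make up the primary endpoint.

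**The case against.** The best defence is that these are wording conflicts with little practical effect. Several parts of it stand.

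- The fill difference is described as slight, and the opacity of capsules and blisters is not stated. Counting from blister strips need not reveal fill, and used capsules have been emptied.
- The opening sentence of 6.4.1 ties the ban to helping the patient with dosing, which could leave collection outside it. The closing sentence of the section carries no such limit, although it does say directly. Clarification is needed on either reading.
- Patients are not told that run-in is placebo, so a change in capsule is ambiguous to them.
- FEV1 is subject to acceptability and repeatability criteria, and the central over-read is final (Sections 8.4.1 and 16.3). This limits bias from effort but does not exclude it.
- SAP Section 4 removes the modelled treatment comparisons for ADSD/ANSD, SABA use and PEF, leaving summaries. The self-reported endpoints that keep treatment contrasts are ACQ-5 and AQLQ+12, both secondary and without multiplicity adjustment.
- The study was terminated early, so few visits may remain to protect.

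These points reduce the likely consequence. They do not make the three sections consistent, and they do not supply the missing argument about run-in exposure.

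**Conclusion.** The point holds as an inconsistency in the blinding procedures with a possible consequence for the blind. The statement on identical appearance is contradicted by the next subsection. The claim of negligible risk omits the run-in. The rules on collecting and counting capsules cannot all be obeyed.

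The size of any bias cannot be computed, because the visibility of the fill difference is not given. The 7/9 share shows how many patients change from placebo to active capsules, and nothing about how many could tell. For patients a visible change would be a hint of allocation; for staff the risk lies in carry-over to later visits.

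A reader might go further and infer that following the plan unblinds patients or assessors, or that bias favours active doses and grows with dose, imitating a dose-response. The documents do not support either inference. They report no actual unblinding, and they do not say how fill is ordered across 0.5 to 8 mg or where placebo falls in that order.

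**What to change.** Reconcile Sections 6.4, 6.4.1 and 6.6.1.

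1. Returned study drug is handed over in a closed, opaque container, through the OHP at off-site visits. Only the existing independent administrator opens and counts it.
2. Section 6.4.1 gains a narrow exception to the bar on other duties: that person may record the count and pass on the count alone.
3. Section 6.4(2) states that treatments are identical except for a slight difference in fill volume.
4. The word negligible is replaced by a justification that addresses run-in exposure. It should say whether the fill is visible in use and whether run-in and double-blind placebo match.
5. The study report gives the possible loss of blinding as a limitation when reading ACQ-5, AQLQ+12 and effort-dependent FEV1, and says who in practice counted capsules.

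One practical detail needs settling. Table 8-1 shows no dispensing at Week 2 and allows some Week 2 assessments off site, so the amendment should say how a kit still in use is counted at that visit.

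The cost is wording, a small extra handling step, and a limited recording task for a person who sees the capsules. That slightly relaxes the separation 6.4.1 was written to protect, which is why only the count should pass. Given early termination, the benefit to remaining visits is limited and the main effect is on reporting.
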